## 5.4 Modification of the Trial and Protocol

Any amendments to this trial plan and protocol must be discussed with and approved by the Sponsor. If agreement is reached concerning the need for an amendment, it will be produced in writing by the Sponsor, and the amended version of the protocol will replace the earlier version. All substantial amendments, e.g., that affect the conduct of the trial or the safety of subjects, require IEC / IRB approval, and must also be forwarded to regulatory authorities.

An administrative amendment to a protocol is one that modifies some administrative or logistical aspect of the trial but does not affect its design or objectives or have an impact on the subjects' safety. Administrative changes do not require IEC / IRB approval; however, the IEC / IRB must be notified whenever one is made.

The Investigator is responsible for ensuring that changes to an approved trial, during the period for which IEC / IRB approval has already been given, are not initiated without IEC / IRB review and approval, except to eliminate apparent immediate hazards to subjects.

## 5.5 Interruption of the Trial

The trial may be discontinued if new data about the investigational product resulting from this or any other trials become available; or for administrative reasons; or on advice of the Sponsor, the Investigators, and / or the IECs / IRBs. If the trial is prematurely terminated or suspended, the Sponsor shall promptly inform the Investigators, the regulatory authorities, and the IECs / IRBs of the reason for termination or suspension, as specified by the applicable regulatory requirements.

The Investigator shall promptly inform the trial subjects and assure appropriate therapy and / or follow-up for them.

# 6 Vaccines Administered

## 6.1 Identity of the Investigational Product

### 6.1.1 Identity of Trial Product (QIV-HD)

The investigational QIV-HD is a split virion quadrivalent influenza vaccine (60 µg HA/strain) containing virus strains chosen by the WHO / VRBPAC for the NH 2017-2018 influenza season. The vaccine contains 2 antigens of type A (H1N1 and H3N2) and 2 antigens of type B (one each from Yamagata and Victoria lineages). Each pre-filled syringe contains a total of 240 µg HA antigen per 0.7 mL dose provided in sterile suspension for IM injection.

When compared to the licensed TIV-HD, the production of QIV-HD uses the same DS and drug product manufacturing processes except for the DP formulation step, which includes the addition of a second influenza B-strain at the same concentration as the other 3 strains (60µg/strain/dose). This also results in a slightly higher fill volume. QIV-HD vaccine is thimerosal-free and prepared from influenza viruses propagated in embryonated chicken eggs.

### 6.1.1.1 Composition

Each 0.7 mL dose of QIV-HD vaccine contains the following components:

*(Strains are based on WHO / VRBPAC recommendations for the 2017-2018 NH influenza season.):*

**Active substances:**

- A/Michigan/45/2015 (H1N1) strain 60 µg HA
- A/Hong Kong/4801/2014 (H3N2) strain 60 µg HA
- B/Brisbane/60/2008 strain 60 µg HA
- B/Phuket/3073/2013 strain 60 µg HA

**Excipients:**

- Buffered saline solution quantity sufficient (qs) to appropriate volume
- Octylphenol Ethoxylate (Triton X-100®) not more than (NMT) 350 µg

Preservative is not used in the manufacture of QIV-HD.

Batch number: TBD

### 6.1.1.2 Preparation and Administration

Vaccination is not to be performed in subjects allergic to one of the constituents of the vaccine.

Prior to administration, all study products must be inspected visually for cracks, broken seals, correct label content (see [Section 6.3.1](#)), and extraneous particulate matter and / or discoloration, whenever solution and container permit. If any of these conditions exists, the vaccine must not be administered. A replacement dose is to be used, and the event is to be reported to the Sponsor.

Subjects must be kept under observation for 30 minutes after vaccination to ensure their safety, and any reactions during this period will be documented in the CRB. Appropriate medical equipment and emergency medications, including epinephrine (1:1000), must be available on site in the event of an anaphylactic, or other immediate allergic reaction.

### 6.1.1.3 Dose Selection and Timing

The vaccination schedule of a single dose for the influenza season is per standard practice for receipt of annual influenza vaccination.

## 6.1.2 Identity of Control Product 1 (Licensed TIV-HD [TIV-HD1])

Fluzone High-Dose Influenza Vaccine (Zonal Purified, Subvirion) (TIV-HD1) is the licensed (in the US) injectable sterile suspension with trivalent inactivated Type A and B influenza split virus vaccine, provided in a pre-filled syringe. It is a sterile suspension prepared from influenza viruses propagated in embryonated chicken eggs.

### 6.1.2.1 Composition

Each 0.5 mL dose of TIV-HD1 vaccine contains the following components:

*(Strains are based on WHO/VRBPAC recommendations for the 2017-2018 NH influenza season.):*

**Active Substances:**

- A/Michigan/45/2015 (H1N1) strain 60 µg HA
- A/Hong Kong/4801/2014 (H3N2) strain 60 µg HA
- B/Brisbane/60/2008 strain 60 µg HA

**Excipients:**

- Buffered saline solution qs to appropriate volume
- Octylphenol Ethoxylate (Triton X-100®) NMT 250 µg

Preservative is not used in the manufacture of licensed TIV-HD1.

Batch number: TBD

### 6.1.2.2 Preparation and Administration

The procedures for preparing and administering the control product are the same as those described for the trial product in [Section 6.1.1.2](#).

### 6.1.2.3 Dose Selection and Timing

The vaccination schedule of a single dose for the influenza season is per standard practice for receipt of annual influenza vaccination.

## 6.1.3 Identity of Control Product 2 (Investigational TIV-HD [TIV-HD2])

The investigational TIV-HD (TIV-HD2) is a High-Dose Influenza Vaccine (Zonal Purified, Subvirion) injectable sterile suspension with trivalent inactivated Type A and B influenza split virus vaccine, provided in a pre-filled syringe. It is a sterile suspension prepared from influenza viruses propagated in embryonated chicken eggs.

### 6.1.3.1 Composition

Each 0.5 mL dose of TIV-HD2 vaccine contains the following components:

*(Strains are based on WHO/VRBPAC recommendations for the 2017-2018 NH influenza season.):*

**Active Substances:**

- A/Michigan/45/2015 (H1N1) strain 60 µg HA
- A/Hong Kong/4801/2014 (H3N2) strain 60 µg HA
- B/Phuket/3073/2013 strain 60 µg HA

*Excipients:*

- Buffered saline solution qs to appropriate volume
- Octylphenol Ethoxylate (Triton X-100®) NMT 250 µg

Preservative is not used in the manufacture of TIV-HD2.

Batch number: TBD

### **6.1.3.2 Preparation and Administration**

The procedures for preparing and administering the control product are the same as those described for the trial product in [Section 6.1.1.2](#).

### **6.1.3.3 Dose Selection and Timing**

The vaccination schedule of a single dose for the influenza season is per standard practice for receipt of annual influenza vaccination.

## **6.2 Identity of Other Products**

Not applicable.

## **6.3 Product Logistics**

### **6.3.1 Labeling and Packaging**

All products for this blinded trial will be administered by IM injection.

All study vaccines will be supplied with investigational labeling and packaging. Each single dose of investigational or control product will be identified by a unique medication number on the label and on the carton. The carton label will also have a detachable label for the sites to attach to the source documents. See the Operating Guidelines for additional label detail.

### **6.3.2 Product Shipment, Storage, and Accountability**

#### **6.3.2.1 Product Shipment**

The Clinical Logistics Coordinator or designee will contact the Investigator or a designee in order to determine the dates and times of delivery of products.

Each vaccine shipment will include a temperature-monitoring device to verify maintenance of the cold chain during transit. On delivery of the product to the site, the person in charge of product receipt will follow the instructions given in the Operating Guidelines, including checking that the cold chain was maintained during shipment (i.e., verification of the temperature recorders). If there is an indication that the cold chain was broken, this person should immediately quarantine

the product, alert the Sanofi Pasteur representative, and request authorization from Sanofi Pasteur to use the product.

#### **6.3.2.2 Product Storage**

The Investigator will be personally responsible for product management or will designate a staff member to assume this responsibility.

At the site, products must be kept in a secure place with restricted access. Vaccines will be stored in a refrigerator at a temperature ranging from +2°C to +8°C. The vaccines must not be frozen. The temperature must be monitored and documented (see the Operating Guidelines) for the entire time that the vaccine is at the trial site. In case of accidental freezing or disruption of the cold chain, vaccines must not be administered and must be quarantined, and the Investigator or authorized designee should contact the Sanofi Pasteur representative for further instructions.

#### **6.3.2.3 Product Accountability**

The person in charge of product management at the site will maintain records of product delivery to the trial site, product inventory at the site, the dose given to each subject, and the disposal of or return to the Sponsor of unused doses.

The necessary information on the product labels is to be entered into the source document and the CRB.

The Sponsor's monitoring staff will verify the trial site's product accountability records against the record of administered doses in the CRBs and the communication from the IRT (if applicable).

In case of any expected or potential shortage of product during the trial, the Investigator or an authorized designee should alert the Sanofi Pasteur representative as soon as possible, so that a shipment of extra doses can be arranged.

#### **6.3.3 Replacement Doses**

If a replacement dose is required (e.g., because the syringe broke or particulate matter was observed in the syringe), the site personnel must either contact the IRT to receive the new dose allocation, or follow the instructions given in the Operating Guidelines.

#### **6.3.4 Disposal of Unused Products**

Unused or wasted products will be returned to the Sponsor in accordance with the instructions in the Operating Guidelines. Product accountability will be verified throughout the trial period.

#### **6.3.5 Recall of Products**

If the Sponsor makes a decision to launch a retrieval procedure, the Investigator(s) will be informed of what needs to be done.

## 6.4 Blinding and Code-breaking Procedures

To ensure that objective data are obtained, the trial is designed as a modified double-blind study as follow:

- The unblinded qualified trial staff member, independent of the safety evaluation and other trial evaluations will administer the vaccine
- The Investigators (or delegates) in charge of safety assessment, the trial staff who collect the safety data, and the laboratory personnel who analyze the blood samples will not know which product was administered
- The subject will not know which product was administered

The Investigator responsible for safety assessment will not attend the vaccination session but will be available in case of emergency (e.g., anaphylactic shock).

Dose numbers will be used to identify each vaccine syringe for the purpose of randomization, vaccination and the recording of vaccine administered. Dose numbers will be randomly assigned to QIV-HD and TIV-HD syringes. The IRT vendor will be responsible for providing the treatment group identification and dose number to be received by the enrolled subject. The subject, the Investigator, and study staff members who collect the safety data and laboratory personnel who analyze the blood samples will all be blinded to the group assignment. The individual responsible for preparing / administering vaccine will not be authorized to collect any safety / serology data.

The code may be broken in the event of an AE only when the identification of the vaccine received could influence the treatment of the subject. Code-breaking should be limited to the subject(s) experiencing the AE.

The blind can be broken by the Investigator or a delegate through the IRT system as explained in the code-breaking procedures described in the Operating Guidelines. Once the emergency has been addressed by the site, the Investigator or a delegate must notify the Sanofi Pasteur RMO if a subject's code was broken. All contact attempts with the Sponsor prior to unblinding are to be documented in the source documents, and the code breaking CRF is to be completed.

A request for the code to be broken may also be made:

- by the GPE Department through an internal system for reporting to Health Authorities in the case of an SAE as described in ICH E2A. In this case, the code will be broken only for the subject(s) in question. The information resulting from code-breaking (i.e., the subject's vaccine or group assignment) will not be communicated to either the Investigator or the immediate team working on the study, except for the GPE representative.

The IEC / IRB must be notified of the code-breaking. All documentation pertaining to the event must be retained in the site's study records and in the Sanofi Pasteur files. Any intentional or unintentional code-breaking must be reported, documented, and explained, and the name of the person who requested it must be provided to the Sponsor.

In any case, the code will be broken after the first database lock, for the primary statistical analysis planned to analyze the data collected within the 28 days following the vaccination, but the randomization list will not be provided to Investigators and will be kept internally until the final database lock.

## 6.5 Randomization and Allocation Procedures

The study will be randomized, modified double-blinded for 3 vaccine groups. Table 6.1 shows the allocation of subjects to each vaccine group. No age stratification is applied here.

**Table 6.1: Enrollment of subjects by vaccine groups and the expanded immunogenicity subsets**

	QIV-HD	TIV-HDs		Total Subjects
	QIV-HD	TIV-HD1 (licensed TIV-HD)	TIV-HD2 (investigational TIV-HD with alternate B strain)	
Subjects to be Enrolled	1744	436	436	2616
Expanded Immunogenicity Subset†	100	100	100	300

\*Safety data and serum for HAI testing will be collected for all subjects.

†A randomized subset of subjects from each group will be selected for SN testing.

For the subject list, block randomization is applied for all subjects within strata by sites. The allocation ratio for the 3 vaccine groups is 4:1:1. Subjects who meet the inclusion / exclusion criteria and sign an ICF will be randomly assigned to one of the groups via IRT. Subjects will also be randomly assigned into the Expanded Immunogenicity Subset for SN testing via IRT. The site administrator will connect to the IRT, enter the identification and security information, and confirm a minimal amount of data in response to IRT prompts. The IRT will then provide the subject number, the vaccine assignment, and have the site administrator confirm it. Subject numbers and dose numbers will be recorded on the source documents and CRBs. The full detailed procedures for randomization are described in the Operating Guidelines. If the subject is not eligible to participate in the study, then the information will only be recorded on the subject recruitment log.

Subject numbers that are assigned by the IRT will consist of a 12-digit string (a 3-digit country identifier, a 4-digit study center identifier, and a 5-digit subject identifier). For example, Subject 840000100005 is the fifth subject enrolled in Center Number 1 in the US (840 being the US country code).

Subject numbers should not be reassigned for any reason.

For packaging list, dose numbers will be 7 digits long. Dose numbers are not used for packaging but only in the IRT system.

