### 11.3 Data Review

A blind review of the data is anticipated through the data review process led by Data Management before database lock.

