#### 12.1.1.1.2 Statistical Methods

Assuming that  $\log_{10}$  transformation of the data follows a normal distribution, the  $\log_{10}$  (data) will be used for the statistical analysis, then antilog transformations will be applied to the results of calculations, in order to provide the results in terms of geometric means (GMs).

The statistical methodology will be based on the use of the 2-sided 95% CI of the ratio of post-vaccination GMTs and difference in seroconversion rates between QIV-HD and TIV-HD groups. The 95% CIs will be calculated by normal approximation of log-transformed titers for GMTs and by the Newcombe-Wilson score method without continuity correction for seroconversion rates. The margins used for non-inferiority hypothesis testing are 1.5 for GMTs and 10% for seroconversion rates based on Food and Drug Administration (FDA) guidelines for licensure of seasonal influenza vaccine (11).

The non-inferiority objective will be achieved only if it is demonstrated for 4 strains and for both GMTs and seroconversion rates. Analyses will be performed for both the Full Analysis Set (FAS) and the Per-protocol Analysis Set (PPAS), but the conclusion will be made from PPAS results.

A sensitivity analysis will be performed with adjustment on the pre-vaccination HAI titers.

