#### *Superiority of QIV-HD to TIV-HD1 or TIV-HD2*

The statistical methodology will be based on the use of the 2-sided 95% CI of the ratio of post-vaccination GMTs and difference in seroconversion rates between the QIV-HD group and TIV-HD group. The 95% CIs will be calculated using normal approximation of log-transformed titers for GMTs and using the Newcombe-Wilson score method without continuity correction for seroconversion rates. For each strain, the 2-sided 95% CI should lie above 1.5 for GMTs and above 10% for seroconversion rates.

The superiority objective will be achieved if the superiority is demonstrated for both B strains and for both GMTs and seroconversion rates. Analyses will be performed for both FAS and PPAS but the conclusion will be made from FAS results.

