### 12.2.3 Per-Protocol Analysis Set

The PPAS is a subset of the FAS. The subjects presenting with at least one of the following relevant protocol deviations will be excluded from the PPAS:

- Subject did not meet all protocol-specified inclusion criteria or met at least one of the protocol-specified exclusion criteria
- Subject did not receive vaccine
- Subject received a vaccine other than the one that he / she was randomized to receive
- Preparation and / or administration of vaccine was not done as per-protocol
- Subject did not provide the post-dose serology sample (V02) in the proper time window (i.e., 28 to 35 days after vaccination) or a post-dose serology sample (V02) was not drawn
- Subject received a protocol-prohibited therapy / medication / vaccine

In addition to the criteria listed above, subjects will also be excluded from the PPAS if their post-vaccination serology sample did not produce a valid HAI test result (i.e., HAI results for all antigens are missing).

The above protocol deviations leading to exclusion from the PPAS may be detailed and completed if necessary in the SAP, following the review of protocol deviations during the study conduct. In any case, the PPAS definition will be finalized before the first database lock.

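### Randomization is blocked within site but the confirmatory GMT intervals carry no site term: valid, slightly too wide if sites differ, and material only for B-strain superiority

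*Protocol*

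**What the plan says.** **Design.** Protocol Section 6.5 allocates 4:1:1 and says that "block randomization is applied for all subjects within strata by sites". Site is the only stratum named; on age the section says "No age stratification is applied here". Section 3 plans about 36 US centers.

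**Primary GMT analysis (Section 12.1.1.1.2).** "The 95% CIs will be calculated by normal approximation of log-transformed titers for GMTs". The one covariate adjustment is secondary in status: "A sensitivity analysis will be performed with adjustment on the pre-vaccination HAI titers".

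**Superiority GMT analysis (Section 12.1.2.1.2).** "The 95% CIs will be calculated using normal approximation of log-transformed titers for GMTs". No adjusted analysis is planned here. Success requires both B strains on both GMT and seroconversion, concluded from the FAS.

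**SAP.** The supplied SAP is an addendum for the ELLA assay that refers to a core body for the main methods. Protocol Section 12.1 assigns the full description of analyses to the SAP, and the core body was not available.

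**The concern.** Blocking within site gives every site close to the same 4:1:1 mix, so site-to-site differences in mean titer largely cancel from the vaccine contrast. A two-group standard error does not reflect this: it uses the total variance, including the between-site part. If that part is not zero, the interval is wider than the design requires and the one-sided error is below the nominal 0.025.

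What is at stake is efficiency. An over-wide interval costs power, and the tested objective with least power to spare is B-strain superiority, at 55.4% in Protocol Section 12.5.

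**Working it through.** **Inputs from Protocol Section 12.5.** 1744 QIV-HD and 436 per TIV-HD group; log10 SD 0.55 for B strains and 0.63 for A strains; superiority at an expected GMT ratio of 1.8 with 5% attrition (FAS); non-inferiority with 8% attrition. The superiority threshold is 1.5 and the one-sided level 0.025. The ICC is not in the documents; 0, 2, 5 and 10% are assumed.

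**1. Reproduce the stated superiority power.**
- n = 1744 × 0.95 = 1656.8 and 436 × 0.95 = 414.2.
- SE = 0.55 × √(1/1656.8 + 1/414.2) = 0.03021.
- d = log10(1.8/1.5) = 0.07918.
- GMT power per strain = Φ(0.07918/0.03021 − 1.96) = Φ(0.661) = 74.6%.
- Seroconversion, reading the assumption as 8% versus 30%: SE = √(0.08×0.92/414.2 + 0.30×0.70/1656.8) = 0.01745; power = Φ(0.12/0.01745 − 1.96), essentially 100%.
- Both strains, treated as independent: 0.7456² = 55.6%, against 55.4% stated. GMT is the binding part.

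**2. Effect of a site term.** Under within-site blocking the true SE of the contrast is about SE × √(1 − ICC). With site in the model, the reported SE matches it. Without site, the reported SE stays at 0.03021.
- With site, per strain: Φ(d/(SE√(1−ICC)) − 1.96).
- Without site, per strain: Φ((d − 1.96 SE)/(SE√(1−ICC))).
- One-sided error without site: Φ(−1.96/√(1−ICC)).

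| Assumed ICC | SE with site, relative | Joint GMT power without site | With site | Gain, points | One-sided error without site |
|---|---|---|---|---|---|
| 0 | 1.000 | 55.6% | 55.6% | 0 | 0.0250 |
| 2% | 0.990 | 55.9% | 56.9% | 0.9 | 0.0239 |
| 5% | 0.975 | 56.4% | 58.8% | 2.4 | 0.0222 |
| 10% | 0.949 | 57.3% | 62.2% | 4.9 | 0.0194 |

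Gains are taken from unrounded powers. A simulation with 36 unequal sites, assumed blocks of 6 and 5% attrition gave SE ratios of 1.001, 0.991, 0.976 and 0.951, and joint power without/with site of 55.7/55.5, 56.0/56.8, 56.4/58.4 and 57.0/61.7%.

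**3. Overlap with baseline titer.** Suppose the superiority model also had pre-vaccination titer, with an assumed within-site correlation of 0.3 to 0.7. At ICC 2, 5 and 10%, adding site would then gain:
- 0.7–1.0, 1.6–2.5 and 3.1–5.1 points if baseline carries none of the site variance;
- 0.3–0.5, 0.8–1.3 and 1.4–2.5 points if it carries half;
- nothing if it carries all.

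**4. Primary objective.** With 8% attrition, n = 1604.5 against 802.2 (A strains, pooled controls) or 401.1 (B strains), and margin log10(1.5) = 0.1761.
- A strains: SE = 0.02724; Φ(4.50) is over 99.99%.
- B strains: SE = 0.03070; Φ(3.78) = 99.99%.
- B-strain seroconversion: Φ(0.1/√(0.4×0.6×(1/401.1 + 1/1604.5)) − 1.96) = 95.5% per strain. This limits the overall figure, which reproduces at 90.8% (90.5% with the Newcombe interval) against 90% stated.

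**5. Variance under 4:1 allocation.** Steps 1 to 4 assume equal SDs. As an illustration, take SD 0.60 in the TIV-HD group and 0.55 in QIV-HD.
- Pooled variance = (1656.8×0.3025 + 414.2×0.36)/2071 = 0.3140, so the reported SE is 0.03078.
- True SE = √(0.3025/1656.8 + 0.36/414.2) = 0.03243.
- One-sided error = Φ(−1.96 × 0.03078/0.03243) = 0.031.

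In simulation an ordinary equal-variance site model gave 0.031–0.033 in this setting; a heteroscedasticity-robust variance gave about 0.024–0.027.

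**The case against.** The case against acting is substantial.

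- **Nothing is invalid.** A reader might infer from blocking without a site term that the intervals under-cover or that type I error is inflated. The opposite holds: with equal SDs the error is at or below 0.025. This stands.
- **The size rests on an assumption.** The ICC is not in the documents, and at zero there is no gain. A single country, a planned three-week inclusion period and HAI assays under one laboratory's responsibility give no sign of large site differences. This stands, and is why a range including zero is shown.
- **The core SAP may already include site.** A reader might infer that the trial has no site-adjusted analysis at all. The documents do not support that; they show only that the protocol text and the ELLA addendum contain none.
- **The primary objective gains nothing material.** This also stands. GMT non-inferiority is far from binding, and the seroconversion analysis that limits overall power is left as planned.
- **Planning inputs matter more.** An SD of 0.54 instead of 0.55 moves joint GMT superiority power from 55.6% to 57.9%, and an expected ratio of 1.75 instead of 1.8 drops it to 36.1%. True, but those inputs are not under the analyst's control and the model is.
- **A site model is not a free swap.** Step 5 of the working shows that an equal-variance model can exceed 0.025 under 4:1 allocation, and the superiority groups differ in B-strain content. This holds and shapes the fix. The planned interval may share the risk, since the protocol does not say whether variances are pooled.

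**Conclusion.** The point holds as an optional efficiency gain, not as an error in the plan. The protocol's GMT intervals ignore the one factor used to stratify randomization. If sites differ in mean titer, they are valid but slightly wide: a site term would cut the SE by 1.0, 2.5 or 5.1% at an assumed ICC of 2, 5 or 10%. The benefit falls on B-strain GMT superiority, at about 0.9, 2.4 or 4.9 points of joint power, and shrinks or vanishes if baseline titer is also modelled and carries the site variance. These figures assume the Section 12.5 inputs, equal SDs, effective balance within site and independent strains. The stated 90% and 55.4% powers do not depend on a site term. Priority is low, and the finding covers only the protocol and the supplied addendum.

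**What to change.** First check the core SAP. If it already has a site term, add a cross-reference in the protocol; if site is left out on purpose, one sentence giving the reason is enough.

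Otherwise, before the first database lock (after which Section 6.4 has the code broken):

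1. For the superiority GMT-ratio interval and, for consistency, the non-inferiority one, specify a log10-titer model with vaccine group and site as fixed effects.
2. State group-specific or heteroscedasticity-robust variance, because of the 4:1 allocation.
3. Fix a rule for pooling small sites while blind. Section 11.3 offers the occasion: "A blind review of the data is anticipated through the data review process led by Data Management before database lock". Section 12.2.3 already sets the same deadline for another definition: "the PPAS definition will be finalized before the first database lock".
4. Keep the unadjusted interval as a sensitivity analysis.
5. Leave the Newcombe-Wilson seroconversion analysis as it is.

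**Cost.** One model term, a variance statement, a pooling rule and the wording, with a protocol change following the route in Section 5.4. No new data are needed, since each subject number contains "a 3-digit country identifier, a 4-digit study center identifier, and a 5-digit subject identifier". In simulation, merging all sites under 30 subjects (6.9 of 36 on average) changed the SE ratio at ICC 10% only from 0.951 to 0.954. At ICC 0 the ratio was 1.000 to 1.001, so an unneeded site term costs almost nothing.
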